#### **4.10.5. Sleep Interference (SI)**

SI is a single-item measure that was developed specifically to quantify sleep interference due to pain. SI has an 11-point response scale (ranging from 0 ‘did not interfere with sleep’ to 10 ‘completely interfered with sleep – unable to sleep due to pain’) and asks patients to select the number that best describes how much their pain has interfered with their sleep over a period of 24 hours.

SI change from Baseline will be analyzed similar the WOMAC A (pain) analysis described in [Section 4.10.1.1](#). All available study visits will be analyzed and presented.

#### **4.10.6. EQ-5D-5L**

For the EQ-5D-5L, the scoring information that is described in the EQ-5D-5L User Guide ([https://euroqol.org/wp-content/uploads/2016/09/EQ-5D-5L\\_UserGuide\\_2015.pdf](https://euroqol.org/wp-content/uploads/2016/09/EQ-5D-5L_UserGuide_2015.pdf)) will be used. The EQ-5D-5L has 2 parts: the EQ-5D descriptive system and the EQ visual analogue scale (EQ VAS). The EQ-5D has five dimensions: mobility, self-care, usual activities, pain/discomfort and anxiety/depression. Each dimension is scored from 1 to 5 (best to worst). The EQ VAS is a single question with the subject’s self-rated health, which is recorded on a vertical, visual analogue scale. The available responses range from “Worst imaginable health state” (0) to “Best imaginable health state” (100). In addition, an index score will be derived using the US value set, as described in the EQ-5D-5L User Guide.

Each dimension of the EQ-5D, the EQ VAS and the index score changes from Baseline will be analyzed similar to the WOMAC A (pain) analysis described in [Section 4.10.1.1](#). All available study visits will be analyzed and presented.

#### **4.10.7. HOOS-QOL subscale**

The HOOS-QOL subscale (<http://www.koos.nu/>) has 4 questions, each of which is assigned a score from 0 to 4. The first questions, “How often are you aware of your hip problem?” is coded as follows: 0=never, 1=monthly, 2=weekly, 3=daily, 4=constantly). The remaining questions are coded as follows: 0=not at all, 1=mildly, 2=moderately, 3=severely, 4= totally. A normalized score (100 indicating no symptoms and 0 indicating extreme symptoms) is

---

calculated using this formula: 100-AVERAGE(Q1-Q4)/4\*100. Scores are calculated at each assessment time point. Imputation rules are as presented in [Section 4.2.8](#).

HOOS-QOL change from Baseline will be analyzed similar the WOMAC A (pain) analysis described in [Section 4.10.1.1](#). All available study visits will be analyzed and presented.

#### **4.10.8. TSQM-9**

The Treatment Satisfaction Questionnaire for Medication (TSQM-9) consists of 9 items with a 5 to 7 point scale for each item. There are 3 domains: global satisfaction, effectiveness and convenience. Each domain will be scored as described in the TSQM-9 User Manual (Version 1.1, October 2018). Instructions for Version 1.4 of the TSQM-9 will be used. The TSQM-9 score at Week 12 for each domain will be analyzed using ANCOVA in the same way as the WOMAC AUE analysis as described in [Section 4.10.1.2](#) except that Baseline TSQM-9 score at Baseline will not be a covariate in the model since TSQM-9 was not administered at Baseline. In addition, a figure will not be produced since there is only one visit.

#### **4.10.9. Sensitivity Analyses**

Additional sensitivity analyses may be performed to examine the effect of missing data, as well as the effect of Baseline imbalance, should one occur.

### **4.11. Safety Analyses**

Safety analyses will be conducted using the SP.

#### **4.11.1. Adverse Events**

AEs will be coded using MedDRA and displayed in tables and listings using System Organ Class (SOC) and Preferred Term (PT).

Analyses of AEs will be performed for those events that are considered treatment emergent, where treatment emergent is defined as any AE with onset after the administration of study treatment, or any event that was present at Baseline but worsened in intensity through the end of the study.

If the start date/time of an AE is partially or completely missing, the date/time will be compared as far as possible with the date/time of the start of administration of study drug. The AE will be assumed to be treatment emergent if it cannot be definitively shown that the AE did not occur or worsen during the treatment-emergent period (worst case approach). The following general rules will be used:

- If the start time of an AE is missing but the start date is complete, an AE will only be excluded as being treatment emergent if the start date is before the date of study drug administration or if the stop date/time is before study drug administration.
- If the start time and day are missing but the start month and year are complete, an AE will only be excluded as being treatment emergent if the start month/year is before the month/year of study drug administration or if the stop date/time is before study drug administration.

- 
- If the start day and month are missing but the start year is complete, an AE will only be excluded as being treatment emergent if start year is before the year of study drug administration or if the stop date/time is before study drug administration.
  - If the start date is completely missing, an AE will be considered treatment-emergent unless the stop date/time is before study drug administration.

AEs will be summarized by patient incidence rates; therefore, in any tabulation, a patient contributes only once to the count for a given SOC or PT.

Summary tables will display the number and percentage of patients who experienced at least one treatment emergent AE (TEAE) in each of the following categories:

- Any TEAE
- Any Serious AE (SAE)
- Any TEAE leading to study discontinuation
- Any TEAE by severity (Mild/Moderate/Severe)
- Any TEAE by relationship
- Any index-hip related TEAE
- Any index-hip related SAE
- Any index-hip related TEAE leading to study discontinuation
- Any index-hip related TEAE by severity (Mild/Moderate/Severe)
- Any index-hip related TEAE by relationship
- Any TEAE related to injection procedure

Separate tabulations will be produced for each of following categories:

- All TEAEs by SOC and PT
- All TEAEs by PT (decreasing frequency of FX006 group)
- All SAEs by SOC and PT
- All TEAEs related to study drug by SOC and PT
- All TEAEs related to injection procedure by SOC and PT
- All TEAEs by maximum severity by SOC and PT
- All TEAEs leading to study discontinuation
- All TEAEs leading to death
- All index-hip related TEAEs by SOC and PT
- All index-hip related TEAEs related to study drug by SOC and PT
- All index-hip related TEAEs by maximum severity by SOC and PT

---

Summaries will be presented by treatment group. Within each treatment group, AEs will be presented by the following time periods:

1. Baseline to Week 12
2. Week 12 to Last Visit

Date and time of onset of TEAE will be used to assign the time periods. TEAEs that occurred on the same day as the Week 12 visit will be counted in the "Baseline to Week 12" time period.

In the summary table for "Any TEAE by SOC and PT", an additional row with the number of events observed will be presented. A patient will be counted once for the number of patients if they have multiple events. The total number of events will be the absolute number of events observed, and a patient will be counted more than once for the event totals if they have multiple events.

In these tabulations, related is defined as any TEAE deemed related to study drug by the investigator. If relationship is missing, it will be imputed as related.

If an event has a TEAE start date that, after imputation rules are applied, is not complete enough to determine the time period in which the TEAE occurred, that event will not be included in the tabulations by study day.

Formal hypothesis-testing of AE incidence rates will not be performed.

By-patient listings of all AEs occurring on-study will be provided as well as for the following, for all patients: patient deaths, SAEs and AEs leading to discontinuation.

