- d. After signing the ICF, patients must stop all restricted medications (other than rescue medication). The washout (at least 5 half-lives) must be completed at least 2 days prior to Screening 2 visit.
- e. Rescue medication will be dispensed to the patient at the Screening visit, and a new bottle will be dispensed at each subsequent visit as needed. Drug accountability will be done at each visit
- f. Pregnancy tests will be done in women of child bearing potential. Serum Pregnancy Test to be collected only at Screening visit. Urine Pregnancy Test to be collected prior to injection of study medication and at EOS (when it occurs)
- g. Aspiration must be attempted prior to all injections. If effusion is detected by fluoroscopy guidance, withdraw to near dryness prior to injection
- h. Via Central Laboratory
- i. To be performed under fluoroscopy guidance
- j. To be completed prior to questionnaires
- k. To be completed after APR and PRR training but prior to any other assessments following the sequence in Table 7-5.
- 1. AEs and concomitant medications will be captured from Day 1 (post injection) to EOS visit.
- m. Visit should be conducted within +/- 3 days from scheduled date.
- n. Screening 1 and Screening 2 visits can be combined into one visit provided the patient does not have a washout from prohibited medications. If there is no washout, please perform APR/PRR first, then the questionnaires in order they are shown on Table 7-6, with the WOMAC being completed after APR/PRR, then all subsequent questionnaires as they are listed for Screening 1.

CONFIDENTIAL Page 48 of 72

Table 7-3: Schedule of Study Assessments for Open Label Extension (OLE) Phase

List of Assessments	Second Injection OLE (Week 12 ⁱ , 16, 20, 24) ^{c,n}	Follow-up (every 4 weeks post 2 nd injection) ^{g,n,o}	EOS for OLE e, g, n, p	
Second Injection Criteria	X			
Physical examination			X	
Index Hip Assessment	X	X	X	
Index Hip X-ray ^b			X	
Vital signs	X ^a	X	X	
Weight and BMI			X	
Hematology, Chemistry ^j			X	
Pregnancy Test ^h	X ^{a, o}		X	
Index Hip Aspiration	X ^{a, f, o}			
IMP administration ^{c, k}	X ^{a, o}			
Rescue Medication dispensing and accountability ^d	X	X	X	
Accurate pain reporting and placebo response reduction training ¹	X	X	X	
WOMAC ^m	X	X	X	
PGIC ^m	X	X	X	
SI, HOOS-QOL, EQ-5D-5L ^m	X	X	X	
AE/SAE & ConMeds	To be collected at every visit and whenever applicable			

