7.9.5. Index Hip Assessment

The index hip assessment will be performed by the blinded assessor at the days indicated in the Table 7-2 and Table 7-3. The index hip will be assessed for tenderness, warmth, redness, swelling, and effusion, limitation on range of motion (directions: flexion, extension, abduction, adduction, internal rotation or external rotation; severity: mild, moderate or severe). If there is a clinically significant finding at the Screening or Day 1 Visit (pre-injection), add to the Medical History. At time points post-injection, if there are new clinically significant findings or findings that worsen for the patient's baseline condition, record as AEs.

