8.2.2. Adverse Events That Occur During the Injection Procedure

If an adverse event occurs during the injection procedure, the Unblinded Injector will record the details of the AE in the patient's chart and provide a full report of the event to the Blinded Assessor in a blinded manner. Any difficulties with the study drug administration should not be reported to the Blinded Assessor unless it is a direct cause of an AE. For any difficulties with the study drug, the Unblinded Injector should refer to the Pharmacy Binder.

CONFIDENTIAL Page 56 of 72

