9.4.4. Safety Analyses

Analysis of Adverse Events

Safety analyses will be performed on the Safety Population. AEs will be coded using MedDRA. Incidences (number and percent) of TEAEs, those events that start after dosing or worsened in severity after dosing, will be presented by treatment group. Incidences of TEAEs will also be presented by maximum severity and relationship to study medication.

Similar presentations will be provided for serious AEs, AEs leading to withdrawal from the study, or AEs leading to death. Analysis of AE data will include examination of the incidence rates of TEAEs and index hip TEAEs following the first dose and second dose, as well as the cumulative incidence of TEAEs after all doses of FX006.

Other Safety Analyses

Laboratory data, vital sign information and X-ray data will be presented as descriptive summary statistics for value and change from Baseline at each individual time point. Categorical variables will be summarized by frequencies and percentages.

CONFIDENTIAL Page 65 of 72

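### The Part I tables of procedure-related events omit timed reactions that start before the drug, the capture rules conflict, and serious events during washout have no recording route

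*SAP*

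**What the plan says.** **Analysis.** SAP 4.11.1 analyses only treatment-emergent events (TEAEs). Its definition has two limbs. The first concerns new events: "treatment emergent is defined as any AE with onset after the administration of study treatment". The second brings in events that were already there, provided they got worse by the end of the study. Protocol 9.4.4 has the same substance for both parts of the study: "those events that start after dosing or worsened in severity after dosing". One of the SAP's planned tabulations is "All TEAEs related to injection procedure by SOC and PT". The overall summary has a matching row, and the table list has Table 14.3.1.5 for it. All on-study adverse events, treatment-emergent or not, go into by-patient listings.

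**Capture.** Table 7-2 footnote l, repeated under SAP Table 1, reads: "AEs and concomitant medications will be captured from Day 1 (post injection) to EOS visit". Protocol section 8 and 8.2 also start monitoring at the first dose, and 8.2 names serious events explicitly. Protocol 8.2.2 says something different: "If an adverse event occurs during the injection procedure, the Unblinded Injector will record the details of the AE in the patient's chart". Under 7.5.8 the injector deals with any clinical event in the procedure suite, and a blinded record goes to the blinded team for entry in the database. Under 7.2 the blinded assessor assesses events that occurred during the procedure.

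**Order of steps.** Protocol 7.9.10 and Table 7-2 footnote g place the aspiration attempt before the injection. Protocol 7.5.10 adds numbing if needed, a needle of 20 gauge or larger, and fluoroscopy using contrast or air.

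**Washout.** Under protocol 7.6.2 and Table 7-2 footnote d, restricted drugs stop after consent, and the washout ends at least 2 days before Screening 2. Screening lasts up to 30 days (7.1.1).

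**The concern.** A table of harms from the injection procedure should cover the whole procedure. Here its entry test is tied to the drug. The steps most likely to cause an immediate reaction without any drug effect (local anaesthetic, needle, aspiration, contrast) come before that point. Difficult injection into the hip is the reason the trial was suspended (protocol 5.2.8), so readers will look to this table for the burden of the procedure.

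The capture rules compound this. A site that follows the schedule footnote may not enter an event that 7.5.8 and 8.2.2 require it to record. The protocol also makes patients stop opioids, centrally acting pain drugs and muscle relaxants, but starts safety monitoring only after that withdrawal is over.

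**Working it through.** No arithmetic is involved beyond the size of Part I (2 × 35 = about 70 patients). The check is to apply the documents' own rules to each kind of event.

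| Event | Recorded? | In the procedure-related tables? |
|---|---|---|
| Onset timed before drug, no later worsening | Yes under 7.2, 7.5.8 and 8.2.2; no under footnote l, section 8 and 8.2 | No; listing only |
| Day 1 onset, start time missing | Same conflict | Eligible, unless its stop date or time precedes the drug |
| Onset before drug, worse after it | Same conflict | Eligible under protocol 9.4.4; under the SAP if it counts as present at Baseline |
| Onset after drug | Yes | Eligible |
| Procedure begun, no drug given | Same conflict | No; outside the Safety Population |
| Event during washout | No provision as an adverse or serious adverse event | No |

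Step by step:

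1. *The procedure starts before the clock.* Aspiration before drug is explicit. Needle placement must precede aspiration. That numbing and contrast also come before the drug is my reading of 7.5.10, which does not number the steps.
2. *The missing-time rule does not close the gap.* It keeps doubtful events only when the start date or time is incomplete. A carefully timed transient reaction is dropped, while the same reaction without a time is kept.
3. *The worsening limb is uncertain for these events.* SAP 4.2.10 sets Baseline at the Day 1 assessment before dosing. A reaction that begins after that assessment but before the drug is not clearly present at Baseline.
4. *The Safety Population needs a full or partial dose* (SAP 3.1), and SAP 4.11 uses it for all safety analyses.
5. *No text covers the washout.* Protocol 8.4.1 requires serious events to be reported within 24 hours but sets no window of its own; 8.2 sets the window, at first dose. For screen failures, 7.4.7 collects only minimal data. What remains is the medical history taken at Screening and updated on Day 1.
6. *Linked gap.* Protocol 8.3.3 asks only for relationship to study medication, and SAP 4.11.1 defines related in the same way. Neither says how an event is assigned to the injection procedure.

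**The case against.** The strongest reply has four parts.

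- **Procedure events are collected.** Protocol 7.2, 7.5.8 and 8.2.2 require it, and all on-study events are listed. This stands: a reader might infer that such events go unrecorded, and the documents do not support that. What remains is conflicting instructions and an incomplete table.
- **Administration may mean the whole procedure.** SAP 4.9 reports the numbing agent and aspirated volume as details of drug administration, and 7.5.10 sets both under the administration heading. On that reading, early reactions could count. But Table 7-2 has separate rows for aspiration and drug administration, and marks aspiration as done before injection. The text is ambiguous at best, which is itself a reason to define the starting point.
- **Both arms undergo the same steps before the drug, and adverse event rates are not tested.** This stands. No bias in the FX006 versus saline comparison is shown. The issue is whether the absolute incidence of procedural harm is complete.
- **Starting collection at first dose is a stated choice, and the Medical Monitor must review safety information from any source (8.5).** This stands in part. That duty covers information received, but nothing tells sites to record or send a serious washout event.

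**Conclusion.** The point holds in a limited form. In Part I, a procedural reaction with documented onset, or documented stop, before the drug and no later worsening is absent from the procedure-related tables. The capture instructions contradict each other and must be reconciled. Serious events between consent and Day 1 have no stated recording route. The effect is probably small. It cannot be estimated, because the documents give no rate for reactions before the drug or for washout events.

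Four stronger readings are not supported:

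- *All 510 planned Day 1 procedures (70 + 440) are affected.* SAP 1.2 and 4.4 limit this SAP to Part I. Part II is to have its own SAP, and protocol 9.4.4 plans no procedure-related table. The 440 come in only if the Part II SAP copies these rules.
- *Second injections are affected.* Events there already follow the first dose, and Table 7-3 collects events at every visit.
- *Procedural complications become baseline through 7.9.5.* That section says "If there is a clinically significant finding at the Screening or Day 1 Visit (pre-injection), add to the Medical History". The Day 1 hip assessment is done before randomization (7.9.2, Table 7-2), so it cannot pick up a complication of the later procedure.
- *The six patients with incomplete administration show the loss.* The Safety Population includes partial doses, and no document identifies a patient who received none. The undosed case is a gap in the rules, not an observed loss.

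**What to change.** 1. **SAP 4.11.1, and the Part II SAP when written.** Count procedure-related events from the start of the injection procedure, meaning the first of numbing, needle placement or aspiration. List any such event in a patient who then receives no drug. State where relationship to the procedure is recorded.
2. **Protocol Table 7-2 footnote l (and its copy under SAP Table 1), section 8 and 8.2.** Reconcile these with 7.5.8 and 8.2.2 so that capture starts at that same point.
3. **Protocol 8.2 and 8.4.1.** Record serious adverse events from consent to Day 1 and show them in a separate pre-treatment listing, outside the TEAE tables.

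The first change can bring Part I events already in the database into the tables. The second and third can help only patients still to be enrolled, which in practice means Part II. The cost is wording and one start-time convention, a few more mostly minor events in both arms, and some serious-event reporting during screening.

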### 4.2. General Statistical Methods and Data Handling

#### 4.2.1. General Methods

All outputs will be incorporated into Portable Document Format (PDF) or Word files, sorted and labeled according to the International Conference on Harmonization (ICH) recommendations, and formatted to the appropriate page size(s).

Tables will be presented as described in the sections below. Summary data will be presented by treatment group. For patient disposition, protocol deviations, demographic and baseline characteristics, OA medical history and study drug exposure, a total group that includes both treatment groups will also be presented. Any exceptions to this are described in the appropriate sections below.

For categorical variables, summary tabulations of the number and percentage within each category (with a category for missing data) of the parameter will be presented.

For continuous variables, the number of non-missing values (n), the mean, median, SD, minimum and maximum values will be presented. 95% confidence intervals (CI) may be provided. Additional statistics may be presented for certain endpoints as described below.

All collected data will be presented in by-patient listings sorted by treatment arm and patient number.

All data listings that contain an evaluation date will contain a relative study day (Rel Day Dose 1). Pre-treatment and post-treatment study days are numbered relative to the day of the first dose of study treatment, which is designated as Day 1. The preceding day is Day -1, the day before that is Day -2, etc.

The sections below describe the intended analysis of the endpoints. Additional sensitivity analyses may be employed in the event of any unforeseen data anomalies or data issues not known at the time of writing this analysis plan.

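### The adverse event tables are split into two periods with no all-period column, so a TEAE of undetermined period can go uncounted and whole-study TEAE incidence is not specified

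*SAP*

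**What the plan says.** SAP 4.11.1 sets the layout of the AE summaries by arm and then by time: "Within each treatment group, AEs will be presented by the following time periods". The first period is Baseline to Week 12 and includes the day of the Week 12 visit. The second, which ends the list, is "2. Week 12 to Last Visit".

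Incomplete start dates are handled twice in that section. The first rule decides whether an event is treatment emergent, and it is conservative: "The AE will be assumed to be treatment emergent if it cannot be definitively shown that the AE did not occur or worsen" in the treatment-emergent period. For the extreme case it adds: "If the start date is completely missing, an AE will be considered treatment-emergent unless the stop date/time is before study drug administration". The second rule comes after the list of tables. It concerns a start date that, even with imputation rules in use, "is not complete enough to determine the time period in which the TEAE occurred". The SAP then gives the consequence for such an event: "that event will not be included in the tabulations by study day".

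Three other statements bear on the point.

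- SAP 4.11.1 adds an event-count row to the table by System Organ Class and Preferred Term, and defines it as a plain count of everything observed. It also promises by-patient listings of all on-study AEs.
- SAP 4.2.1 says that "a total group that includes both treatment groups will also be presented", but only for disposition, protocol deviations, demographics and baseline characteristics, OA history and exposure. That total pools the arms, not the periods, and AE tables are not named.
- Protocol 9.4.4 commits to the number and percentage of patients with TEAEs by treatment group, and makes no exception for incomplete dates.

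**The concern.** An event can pass the first rule and be counted nowhere under the second. It is a TEAE, but the only tabulations described are by period, and it is excluded from those. Section 4.11.1 is otherwise conservative (a missing relationship to study drug is imputed as related), whereas this exclusion lowers the counts.

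The layout has a further consequence that needs no missing dates. A patient with events in both periods appears in both columns, so the columns cannot be added. The whole-study proportion of patients with any TEAE, any SAE or any index-hip event is the basic safety summary, and no specified table supplies it. Part I patients could be followed to Week 24 or until the amendment (SAP 2.1), so the second period can hold data.

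**Working it through.** The plan states no figure on this point, so there is none to reproduce. The check applies the rules to each pattern of missing date and then scales the result.

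**1. What the exclusion covers.** No AE tabulation by study day is described in SAP 4.11.1 or in the titles of Tables 14.3.1.1 to 14.3.1.12. The only time-based AE layout is the two-period split, so the exclusion must refer to it. No title or sentence names an overall or period-undetermined column.

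**2. Which events are affected.** Assume onset after dosing and no other information that settles the period. Every pattern below is then a TEAE under the first rule. Take the Week 12 visit at day 84 after dosing and the last visit at day 84 or day 168. Spread onsets evenly over follow-up and dosing dates over 365 days. With follow-up to day 168 there are 169 possible onset days (0 to 168), hence 365 × 169 = 61,685 combinations.

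- Full date: the period is always known (0% undetermined).
- Day missing: the period is unknown if the onset month contains the Week 12 visit and that visit is not on the month's last day. A month of L days gives L(L − 1) such combinations. The sum is 7×31×30 + 4×30×29 + 28×27 = 6,510 + 3,480 + 756 = 10,746, and 10,746/61,685 = 17.4%.
- Day and month missing: the period is known only when a new year falls within follow-up and separates the possibilities. Let b be the number of days from dosing to 1 January. For b = 1 to 84, b onset days are determinable (sum 3,570). For b = 85, all 169 are. For b = 86 to 168, 169 − b are (sum 3,486). The total is 7,225, so (61,685 − 7,225)/61,685 = 88.3% are undetermined.
- Date wholly missing: 100% undetermined.

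If the last visit is Week 12, only one period is possible and the share is 0% for every pattern.

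**3. Size per patient.** SAP 4.1 gives about 35 patients per arm. Each patient whose only TEAE is dropped moves the any-TEAE incidence by 1/35 = 2.9 points; two patients move it by 5.7 and three by 8.6. For scale, Protocol 5.2.7 reports TEAEs in 46.0% of FX006-treated knee patients. Of 35 patients that is 0.460 × 35 = 16.1, or about 16. Dropping one changes 16/35 = 45.7% to 15/35 = 42.9%.

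**4. Whole-study count.** If a patients have a TEAE in the first period, b in the second, and the arm has n patients, the number with any TEAE lies between max(a, b) and min(a + b, n). The two columns alone do not fix it.

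**The case against.** The strongest reply is that the exclusion is confined to time-based tabulations, so it removes nothing from tables that are not split by time, and the text hints at such tables. SAP 4.11.1 says first that summaries are by treatment group and only then adds the periods. The titles of Tables 14.3.1.1 to 14.3.1.12 name no period. The event total is to be everything observed. SAP Section 5 records no departure from the protocol's commitment on TEAE incidence. The table shells are not in the documents. This much stands: an overall column is not forbidden, only not specified. But these hints show that the sentence conflicts with its surroundings; they do not tell a programmer to produce the column.

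It is also fair to say that the trigger is narrow. It needs an incomplete date, follow-up past Week 12, and no stop date or visit record that settles the period. AEs are reviewed at every visit (Protocol 7.9.15), which should keep wholly undated events rare. All AEs remain in the listings, Part I is exploratory, and no AE rates are tested. These points limit the size of the problem and do not remove it.

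A reader might go further and infer that the exclusion contradicts the SAP's worst-case rule. It does not: that rule decides whether an event is treatment emergent, and says nothing about which post-dose period it belongs to. A reader might also set 2.9 points against the SAE rates in Protocol 5.2.7 (1.9% for FX006, 1.1% for placebo). That is not like for like. SAEs are reported within 24 hours of awareness (Protocol 8.4.1) and listed separately, and they are the events least exposed to this rule. The relevant comparison is with the TEAE rates.

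**Conclusion.** Wrong as written, of minor severity. Followed literally, SAP 4.11.1 can leave a TEAE out of the incidence tables, and it specifies no whole-study count of patients with any TEAE. Both sit badly with Protocol 9.4.4, and the first also with the SAP's own definition of the event total.

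The documents do not support saying that safety incidence will be undercounted, or that these events disappear from the report. The missing column is inferred from silence, the listings keep every event, and the number of incompletely dated AEs is not given. The shares of 17.4%, 88.3% and 100% rest on evenly spread onsets, follow-up to day 168 and no other dating information. They describe events that already have incomplete dates, not all TEAEs. The 2.9 points per patient applies to the any-TEAE row only if the dropped event is that patient's sole TEAE, and it uses the planned 35 per arm. The lack of a de-duplicated whole-study count depends on none of these assumptions.

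**What to change.** Add an Overall (all-period) column to every AE table, counting all TEAEs and each patient once per row. This settles both problems.

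Keep events of undetermined period out of the two period columns, and give their number by arm in a footnote. Forcing them into Baseline to Week 12 is not recommended, because it could place late events in the double-blind period.

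Reword the exclusion so that it refers to tabulations by time period and states that the events are included in the Overall column. In the same sentence, drop or define the reference to imputation rules: SAP 4.11.1 classifies incompletely dated events as treatment emergent or not, but imputes no AE start date.

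The cost is one table column and one sentence, with no new data collection.
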